#### 3.1 Investigator Training

Training sessions in proper surgical technique and trial performance for the Principal Investigator, all Sub-Investigators and research coordinators will be provided by the sponsor prior to initiation of the study at each site.

## 4 STUDY METHODS

### 4.1 Study Design

Prospective, non-randomized (single-arm) multi-center study to evaluate the incidence of complications and the patient effectiveness outcomes using the RAVINE system as compared to the literature reported complications and outcomes for the XLIF system when utilized in the surgical treatment of symptomatic DDD with up to Grade 1 spondylolisthesis. If required, supplemental stabilization may be achieved using the SERENGETI posterior percutaneous retractor system, the CAYMAN Minimally Invasive Plate System, or another appropriate minimally invasive (percutaneous or mini-open) system.

### 4.2 Treatment Group

Patients treated with the RAVINE system that had:

- A diagnosis of DDD with up to Grade 1 spondylolisthesis at L2-S1, confirmed clinically and radiographically, requiring surgical intervention
- One or two contiguous levels requiring surgical intervention
- Inadequate response to conservative medical care over a period of at least 6 months
- An age at time of enrollment of  $\geq 18$  years old

### 4.3 Control Group

Literature reported outcomes of adult patients ( $\geq 18$  years old) with lumbar DDD between L2-S1 who presented with up to a Grade 1 spondylolisthesis at one or two contiguous levels, for whom the NuVasive XLIF far-lateral system was used during their surgical intervention.

### 4.4 Sample Size

Two-hundred twenty-two (222) total subjects at up to 15 clinical sites. Sites are considered a Principal Investigator and their Sub-Investigators who are covered by a single Institutional Review Board's (IRB's)/Ethics Committee (EC) oversight and approval.

Subject enrollment will be capped so that no single site contributes more than approximately 20% of cases.

## 5 STUDY OBJECTIVES/OUTCOMES

### 5.1 Primary Effectiveness Objective

The primary effectiveness objective is:

To evaluate the improvement of the Back VAS and the Leg VAS at 24 months as compared to pre-op time periods. Information on all reports of pain/numbness/tingling and the location of symptoms will be captured and evaluated.

### 5.2 Primary Safety Objectives

The primary safety objectives are:

- The evaluation of all adverse events including device related, procedure related and additional serious adverse events.
- Additional surgical intervention at the operative site including the need for removals, revisions, re-operations or supplemental fixation required to modify the device
- The incidence and severity of any psoas muscle injury, genital femoral nerve injury and lumbar injury will be determined for all patients

All adverse events will be documented on a continuous basis and reviewed by K2M Clinical Research Staff. Information regarding all device failures including instrument breakage, implant breakage, subsidence, migration, or expulsion will be captured.

#### 5.2.1 Device and Procedure Related Adverse Events

Device and procedure related adverse events will be documented and reported to the sponsor, including the need for removals, revisions, re-operations or supplemental fixation required to modify the device.

### 5.3 Secondary Objectives

Secondary objectives are expected to further define the safety and patient outcomes for effectiveness of the K2M device. Secondary objectives include:

#### 5.3.1 Visual Analog Scales

The severity of back, hip/buttock, and leg pain will each be evaluated in all study subjects using a 10-cm visual analog scale (VAS).

#### 5.3.2 Incidence of Thigh Pain/Dysesthesia

A neurological evaluation of the patient, with specific evaluation of psoas muscle weakness, radiating radicular pain, knee extension weakness, dorsiflexion weakness, plantarflexion weakness and anterior thigh numbness will be performed by the healthcare staff and will also be addressed through a patient questionnaire entitled Patient Symptom Questionnaire.

#### 5.3.3 Oswestry Disability Index

The Oswestry Disability Index (ODI) is one of the principal condition-specific outcome measures used in the management of spinal disorders. The ODI is the most commonly outcome measures in patients with low back pain. It has been extensively tested, showed good psychometric properties, and applicable in a wide variety of settings. This patient-reported outcome measure is a 10 item questionnaire that evaluates disability and functional impairment associated with back problems. This validated instrument includes items that relate to subjective symptomatology and activities of daily living (pain intensity, personal care, lifting, walking, sitting, standing, sex life, traveling). Each item is scored from 0 up to 5, with higher scores corresponding to greater disability. A total

ODI score is determined by adding the scores of the individual questions and dividing that total by the maximum possible score (i.e., 50 if all questions are answered) to yield a percentage. Therefore, the ODI score ranges from 0% to 100%. An improvement by at least 15 percentage points will be considered a success.

#### 5.3.4 Health-Related Quality of Life

Health-related quality of life will be evaluated in all study subjects using the SF-12v2 Health Survey. This shortened and simplified version of the SF-36 makes the questionnaire less ambiguous for patients. It has a self-administered form that makes it easy to read and complete, and that reduces missing responses. The physical and mental component summary scales, referred to as PCS-12 and MCS-12 will be evaluated against published normative values and a 15% improvement in these scores will be used as an assessment of success. To calculate the true value of a treatment, the scores from the SF-12v2 will be converted into a utility index (SF-6D), which considers not only how many years a medical intervention can add to a patient's life, but also the quality of that life. Use of the SF-6D does not expand the questions administered to the patient.

#### 5.3.5 Radiographic Assessments

Quantitative and qualitative radiographic assessment of the pre and post-operative AP, and Lateral, Flexion/Extension images will be performed and submitted. Radiographic assessments being performed include:

- Qualitative Assessment
  - Device Condition
  - Device Subsidence
  - Device Migration
- Radiographic Assessment of Fusion/Non-fusion
  - Bony Bridging
  - Radiolucency
  - Development of Pseudoarthrosis

#### 5.3.6 Patient Satisfaction

At the 12 month and 24 month follow-up visits, subjects will be asked whether they were satisfied with the outcome of their surgery (Yes/No) and whether they would repeat the operation (Yes/No).

#### 5.3.7 Odom's Criteria

At the 24 month follow-up visit, the Investigator will rate the clinical disposition of each study subject according to Odom's Criteria as follows:

**Excellent:** all pre-operative symptoms relieved, able to carry out daily occupations without impairment.

**Good:** minimum persistence of pre-operative symptoms, able to carry out daily occupations without significant interference.

**Fair/Satisfactory:** relief of some pre-operative symptoms but physical activity is significantly limited.

**Poor:** symptoms or signs unchanged or worse.

#### 5.3.8 Surgery Time

The length of the surgical procedure from the initial incision to final closure will be captured from the Anesthesia Record.

#### 5.3.9 Anesthesia Time

The length of time the patient is under anesthesia will be captured from the Anesthesia Record.

#### 5.3.10 *Estimated Blood Loss*

The amount of blood loss over the entire length of the surgery, documented on the Anesthesia Record, will be captured.

#### 5.3.11 *Neuromonitoring*

The type(s) and any abnormal result(s) of neuromonitoring systems utilized during the surgery will be captured.

#### 5.3.12 *Length of Hospital Stay*

The length of hospital stay from the date of hospital admission to the date of discharge will be calculated.

#### 5.3.13 *Return to Work/School*

The ability to and the time it takes for the subject to be cleared to return to work/school from the date of surgery will be documented.

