#### 8.2.1 Pre-Operative Assessment

- Informed Consent
- Inclusion/Exclusion Criteria
- Demographics
- Pertinent History and Physical including Current Symptoms, Height, Weight, and Tobacco Use

- Work/School Status
- Current Medication for Spine Problem
- Neurological Examination
- AP and Lateral X-rays
- Back, Hip/Buttock, and Leg VAS
- Oswestry Disability Index
- SF-12v2
- Patient Symptom Questionnaire
- Adverse Event assessment

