##### 8.4.1 Follow-Up Evaluations and Data – Post-Op through 24 Months

- Work/School Status (including release for return to work/school) (all visits)
- Current Symptoms (all visits)
- Medication (taken for spine problem since last contact) (all visits)
- Neurological Examination (all visits)
- AP and Lateral X-rays (6 Month, 12 Month, and 24 Month visits)
- Flexion/Extension X-rays (12 Month and 24 Month visits)
- Fusion Assessment (per X-rays and/or CT Scan as determined by the investigator)
- Back, Hip/Buttock, and Leg VAS (all visits)
- Oswestry Disability Index (all visits)
- SF-12v2 (all visits)
- Adverse Event assessment (all visits)
- Patient Symptom Questionnaire (all visits)
- Patient Satisfaction (12 and 24 Month visits only)
- Odom’s Criteria (24 Month visit only)
- Study Exit

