### 12.3 Sample Size

A total sample size of 222 subjects was selected for the study. Assuming the true mean difference between pre-op and 24 month follow-up VAS is 3.66 and the standard deviation is 2.0, a sample size of 189 subjects provides >87% power to detect a statistically significant difference between the mean post-op VAS and the OPC of 3.25 using a one-sided one-sample t-test at a significance level of 0.05. In order to account for approximately 15% attrition, based on clinical experience, 222 subjects will be enrolled.

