### 12.7 Supplementary Analysis

Other ancillary variables such as demographics, baseline variables, surgical variables and post-op pain medication usage will be summarized by mean, standard deviation, median (if appropriate), and range for continuous measures, and frequency and percent for categorical measures.

Graphical methods such as bar graphs, box and whiskers plots, and star plots may be employed to compare the study groups simultaneously for multiple variables.

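### Time to return to work/school has no censoring rule or denominator, and the only generic summary rule could use cleared subjects alone

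*Combined protocol and SAP*

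**What the plan says.** Return to work/school is listed among the effectiveness measures in the synopsis (section 1) and is a numbered secondary objective. Section 5.3.13 says what is to be documented: "The ability to and the time it takes for the subject to be cleared to return to work/school from the date of surgery". That is two items, whether the subject can return and how long clearance takes. No summary statistic is named.

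Status is recorded before surgery (8.2.1, "Work/School Status"). Status and release for return are recorded at every follow-up visit (8.4.1). Follow-up lasts 24 months (7.4), and 12.3 allows for "approximately 15% attrition".

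Section 12 does not mention return to work. The missing-data rules in 12.5 (substituting the 12-month value, and LOCF) concern Back and Leg VAS only. For everything that is neither primary nor safety there is one sentence, in 12.7. It covers "Other ancillary variables such as demographics, baseline variables, surgical variables and post-op pain medication usage", which "will be summarized by mean, standard deviation, median (if appropriate), and range for continuous measures, and frequency and percent for categorical measures".

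**The concern.** Time from surgery to clearance is right-censored. Some subjects may never be cleared within 24 months and some will leave before clearance; neither group has a number to average. The generic sentence in 12.7 suits a fully observed variable such as age or blood loss. Applied to clearance times, it conditions on having been cleared. The error then has a known direction, towards fast recovery, and the median that 12.7 also allows does not cure it, because that median too is taken among the cleared.

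The denominator is open as well. Nothing limits the analysis to subjects who were in work or school before surgery. A retired subject could be left out or counted as not returned, and the percentage able to return would differ accordingly.

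At stake is the reading of one descriptive recovery outcome. Section 2.2 gives quicker recovery and return to function as general background for minimally invasive surgery, so readers may take an interest in this figure.

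**Working it through.** **Inputs from the documents.** Follow-up of 24 months (7.4); about 15% attrition, 222 enrolled and 189 evaluable (12.3); summary statistics from 12.7. **Not in the documents:** the share never cleared and the distribution of clearance times. Both are assumptions below, for subjects who have a job or school place to return to.

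**1. The plan's own figures.** None is stated for return to work. The 12.3 figures reproduce: 222 × 0.85 = 188.7, about 189; and a difference of 3.66 − 3.25 = 0.41 with SD 2.0, n = 189 and one-sided alpha 0.05 gives 87.8% power (noncentral t), against the stated figure of over 87%. Neither uses return to work.

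**2. Who supplies a time.**

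| Subject | Clearance time for a 12.7 summary? |
|---|---|
| Cleared while under follow-up | Yes |
| Not cleared by 24 months | No |
| Lost or withdrawn before clearance | No |
| Not in work or school before surgery | No rule given |

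**3. Effect of the never-cleared share.** Let p be the share never cleared and F the distribution of times among those who can be cleared. The all-subject median t solves (1 − p)F(t) = 0.5, so F(t) = 0.5/(1 − p). With log-normal times, median 3 months and log-SD 0.6, t = 3·exp(0.6·z), where z is the normal quantile of 0.5/(1 − p).

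| p | 0.5/(1 − p) | z | All-subject median (months) | Median among cleared (months) |
|---|---|---|---|---|
| 5% | 0.526 | 0.066 | 3.1 | about 3.0 |
| 10% | 0.556 | 0.140 | 3.3 | about 3.0 |
| 20% | 0.625 | 0.319 | 3.6 | about 3.0 |
| 30% | 0.714 | 0.566 | 4.2 | about 3.0 |

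Simulation of 400,000 subjects per scenario, with 15% lost uniformly over 24 months, gives a median among the cleared of 2.97 to 2.98 months and a mean of 3.55 to 3.56 months at every p. The cleared-only figures do not respond to p.

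**4. A different distribution.** Exponential times, exponential dropout reaching 15% at 24 months, and p = 0, 10, 20 and 30%:

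| Median among clearable subjects | Median among cleared | Kaplan-Meier median, all subjects |
|---|---|---|
| 3 months | 2.9 at every p | 3.0 / 3.5 / 4.3 / 5.4 |
| 6 months | 5.2 at every p | 6.0 / 7.0 / 8.5 / 10.9 |

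The pattern is the same; the gap is wider when recovery is slower.

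**5. Dropout alone (p = 0).** With the log-normal times, the mean among the cleared is 3.54 months against a 24-month restricted mean of 3.58. With exponential times of median 3 months it is 4.13 against 4.31, and with median 6 months 6.83 against 8.10. Most of that last gap comes from the end of follow-up. The exponential mean is 6/ln 2 = 8.66 and the share uncleared at 24 months is 2^(−4) = 0.0625. With no dropout at all, the mean among those cleared would be 8.66 − 24 × 0.0625/0.9375 = 7.06. Dropout takes it only from 7.06 to 6.83.

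**The case against.** The strongest reply is that the plan is silent here rather than wrong. A reader might infer that it prescribes a mean over cleared subjects. It does not: 5.3.13 says only that the items are documented, 12.7 does not name return to work, and no text says to drop uncleared subjects. This stands. What remains is that the list in 12.7 is open-ended and no other rule is available, so an analyst who follows the document is led to a summary that does not suit this variable.

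A reader might also infer that two cohorts with very different return rates would look identical in the report. That goes too far. The ability to return is a separate item, and under 12.7 it would be shown as a frequency and percent. The time summary would still not respond to the return rate, and the percentage itself lacks a denominator and a rule for lost subjects.

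A larger size is tempting too. Under the log-normal assumptions the 24-month restricted mean rises from 4.6 to 9.7 months as p goes from 5 to 30%. But this is roughly (1 − p) × 3.58 + 24p: 3.40 + 1.20 = 4.60 at 5%, and 2.51 + 7.20 = 9.71 at 30%. Nearly all of the rise is the assumed share multiplied by 24 months. It restates the assumption, and it is not the quantity that the fix would report.

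Nor does the planned attrition by itself carry the point; step 5 shows that its effect is small.

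Finally, this is one of many secondary outcomes, with no hypothesis, threshold or literature comparator. That stands and sets the weight.

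**Conclusion.** The point holds as a gap with a predictable consequence. No censoring rule or denominator is stated for time to return to work/school, and the one generic rule that could apply can use only observed clearance times, which biases the summary short. Under log-normal times with median 3 months and log-SD 0.6, the understatement of the median runs from about 0.1 month at 5% never cleared to about 1.2 months at 30%. It is larger if clearance is slower, and close to nil if almost everyone is cleared well before 24 months. The share and the distribution are assumptions, so the direction is firm and the size is not. Severity is low: the outcome is descriptive, and the primary VAS test, the performance criterion and the sample size are untouched.

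**What to change.** Add to 12.7:

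- Analyse time from surgery to clearance by Kaplan-Meier among subjects in work or school before surgery, censoring those not cleared at their last contact.
- Report the cumulative proportion cleared at 3, 6, 12 and 24 months with 95% confidence intervals, and the median if it is reached.
- Tabulate subjects not in work or school before surgery separately.

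Censoring at last contact assumes that subjects who are lost would have been cleared at the same rate as those who remain; the report should say so.

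The cost is one or two sentences. Pre-operative status, and status and release at each visit, are already scheduled, so no extra visits or subjects are needed. It is worth confirming that the follow-up form captures the date of release, since 5.3.13 needs it in any case. The downside for the sponsor is that the reported time may look less favourable.

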#### 5.3.14 *Use of Narcotics Post-Surgery*

The types and dosages of any narcotics taken by the patient post-surgery will be documented.

CONFIDENTIAL DO NOT COPY

## 6 STUDY ENDPOINT

### 6.1 Primary Study Endpoints

The primary effectiveness endpoint is the improvement Back VAS and Leg VAS at 24 months as compared to pre-op time periods.

CONFIDENTIAL DO NOT COPY

## 7 STUDY POPULATION

### 7.1 Sample Size

Two-hundred twenty-two (222) total subjects at up to 15 clinical sites, geographically distributed throughout US.

### 7.2 Inclusion and Exclusion Criteria

To be eligible to participate in the study, a subject must meet all of the Inclusion Criteria and none of the Exclusion Criteria.

#### Inclusion Criteria

1. Diagnosis of DDD with up to Grade 1 spondylolisthesis, confirmed clinically and radiographically, requiring surgical intervention at one or two contiguous levels between L2-S1
2. Inadequate response to conservative medical care over a period of at least 6 months
3. Willing and able to comply with the requirements of the protocol including follow-up requirements
4. Willing and able to sign a study specific informed consent
5. Skeletally mature and  $\geq 18$  years of age at the time of enrollment

#### Exclusion Criteria

1. Active systemic infection or infection at the operative site
2. Co-morbid medical conditions of the spine or upper/lower extremities that may affect the lumbar spine neurological and/or pain assessment
3. Metabolic bone disease such as osteoporosis that contradicts spinal surgery
4. History of an osteoporotic fracture
5. History of an endocrine or metabolic disorder (e.g., Paget's disease) known to affect bone and mineral metabolism
6. Taking medications that may interfere with bony/soft tissue healing including chronic steroid use
7. Known allergy to titanium, cobalt chrome or PEEK
8. Rheumatoid arthritis or other autoimmune disease or a systemic disorder such as HIV, active hepatitis B or C or fibromyalgia
9. Current medical condition (e.g., unstable cardiac disease, cancer) that may result in patient death or have an effect on outcomes prior to study completion
10. Pregnant, or intend to become pregnant, during the course of the study
11. Severe obesity (Body Mass Index  $> 40$ )
12. Physical or mental condition (e.g., psychiatric disorder, senile dementia, Alzheimer's disease, alcohol or drug addiction) that would interfere with patient self-assessment of function, pain or quality of life
13. Involved in current or pending spinal litigation where permanent disability benefits are being sought
14. Incarcerated at the time of study enrollment
15. Current participation in an investigational study that may impact study outcomes

#### 7.4 Study Duration

Study subjects will be expected to participate in this study for 24 months following surgery, with follow-up evaluations at initial post-op, 3 months, 6 months, 12 months, and 24 months.

CONFIDENTIAL DO NOT COPY

## 8 STUDY ENROLLMENT/EVALUATIONS

### 8.1 Patient Screening and Enrollment

Consecutive patients who potentially meet the study inclusion and exclusion criteria will be screened for eligibility. Diagnostic imaging studies to confirm the diagnosis of DDD with up to Grade 1 spondylolisthesis between and including the levels of L2-S1, must be completed within 180 days of the planned date of surgery (provided there have been no significant changes in the patient's clinical presentation). If, at an interim point following the initial imaging, and prior to surgery, the subject experiences a significant change in his/her clinical presentation, the changes should be documented and the images repeated. Patients will be screened as follows:

- Consecutive patients are potentially eligible for entry into the study based on their age and whether their medical condition appears to generally fit the characteristics specific to this study.
- Patients who agree to enter the study must sign the approved informed consent form.
- A patient is considered enrolled in the study after signing the IRB/EC approved informed consent. Consented patients complete the remainder of the screening process to confirm study eligibility. Patients who do not fulfill the screening criteria are considered Screening Failures and will be documented on the Screening & Enrollment Log. Screening failures will not count against the total number of subjects eligible for analysis.
- Subjects who have signed the informed consent and fulfilled the Inclusion/Exclusion criteria are then scheduled for surgery. It is important that surgery be scheduled within 90 days from the date that the subject completed the required pre-operative questionnaires for the study and within 180 days from the date of the required pre-operative X-rays (provided there have been no significant changes in the patient's clinical presentation). The following should be considered when evaluating whether or not the change in clinical presentation is considered significant: an increase in related pain of approximately 3 points (on VAS scale from 0-10), a change in the location of the pain, deteriorating neurological status or other conditions where repeat radiographic studies may be necessary. The objective is to ensure that the patient still meets the eligibility criteria based on the medical judgment of the surgeon.

Once a patient is enrolled into the study, they will need to be given a unique subject identifying number (Subject ID) that will be used to capture de-identified information. For this study, the following standardized format will be used: *Site Identifying Number (2 digits)-Subject Identifying Number (3 digits)*. Your site identifying number will be assigned by the Sponsor, and the subject identifying number should start with 001 and continue accordingly during patient enrollment. For example, if the site identifying number issued to you is Site 03, and you are enrolling your second patient into the study, their Subject ID would be 03-002. A Patient Information Log will be provided to you to keep as a cross reference for study subjects.

